The investigational product (IP) is amifampridine, and it will be provided in round, white-scored tablets, containing amifampridine phosphate formulated to be the equivalent of 10 mg amifampridine base per tablet. Dosing is up to 80 mg/day in 3 or 4 divided doses.

The investigational product, and matching placebo, will be provided by Catalyst Pharmaceuticals, Inc., [name].

REFERENCE THERAPY, DOSE, ROUTE, AND REGIMEN:

The reference therapy is a placebo, provided as tablets indistinguishable from amifampridine tablets. The placebo will be administered consistent with the dose and dose regimen of the investigational product (amifampridine).

DURATION OF TREATMENT:

Approximately 8 weeks (depending on length of dose titration and excluding up to 14-day screening period). The Run-in phase requires that the patient must be on a stable dose and regimen of amifampridine for the last week of Run-in.

CRITERIA FOR EVALUATION:

Safety:

Safety will be assessed by the incidence of treatment-emergent adverse events (TEAEs), including serious adverse events (SAEs). Vital signs, 12-lead ECGs, clinical laboratory tests, physical examination, and concomitant medications will also be evaluated.

Efficacy:

Efficacy will be assessed by comparison of amifampridine versus placebo for:

Primary -

• Change from baseline in HFMSE total score;

Secondary -

- Change from baseline in quality of life assessments (INQoL or PEDSQoLTM).
- Change from baseline in 6-minute walk test.
- Timed items (rising from floor, rising from a chair, climbing 4 steps, walking 10 meters).

STATISTICAL METHODS:

Sample Size Determination

The sample size for this study is based on clinical considerations related to the epidemiology of the disease, and not on a formal statistical power calculation. The sample size should be representative of a sufficient number of patients to evaluate the study objectives (i.e. safety, tolerability, and evidence of efficacy of amifampridine in the target population). It is anticipated approximately 12 patients will be randomized.

Page 7

Safety Analysis

Safety analyses will be conducted on the safety population (i.e. all patients who receive at least 1 dose of amifampridine). The safety analysis will be descriptive and will be presented on observed data only.

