8.1.2 Secondary Objective

The secondary objective of the study is:

 To assess the clinical efficacy of amifampridine compared with placebo by using the change from baseline in six-minute walk test, timed tests, and quality of life assessments;

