14.6.2 Secondary Efficacy Endpoint Analyses

The quantitative secondary efficacy endpoints (6-minute walk test, Time-to-rise-from-floor, Time-to-rise-from chair, Time-to-climb-4-stairs, and Time-to-walk-10 meters) will be analyzed as the HFSME is analyzed. The four CFB scores will be analyzed with a linear mixed model. Treatment and Sequence will be entered as fixed effects. Subject within Sequence will be entered as a random effect with a block-diagonal covariance structure. Population marginal means will be estimated for each of the four Period and Sequence combinations.

Results from INQoL questionnaires and PEDSQL TM inventory of disease specific symptoms will be summarized with descriptive statistics (n, mean, standard deviation, minimum, median, and maximum) per time point (Days 0, 7, 14, 21, and 28) and CFB, using the Day 0

¹ Also known as "LSMEANS".

Page 56

response as the baseline level). The subscales of the QoL questionnaires will be similarly summarized.

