# 5 Trial Design

## 5.1 Study Objectives

The primary objectives of the study are:

• To characterize the overall safety and tolerability of amifampridine compared with placebo in patients with SMA Type 3; and

 To assess the clinical efficacy of amifampridine compared with placebo in ambulatory patients with SMA Type 3 based on change from baseline in the Hammersmith Functional Motor Scale Expanded (HFMSE) scores.

The secondary objective of the study is to assess the clinical efficacy of amifampridine compared with placebo by using the change from baseline in six-minute walk test, timed tests, and quality of life assessments:

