### 10.2 General Statistical Considerations

The following standards will be applied for the analyses unless otherwise specified.

Simple summary statistics (descriptive statistics) for continuous data will be n (number of non-missing observations), mean, median, standard deviation, minimum, and maximum.

The frequency count and percentage will be used to summarize categorical data. Summary statistics will be presented by treatment by period and overall.

Summary statistics for all safety and efficacy variables will be presented by sequence, except for tables related to incidence of AEs which will be presented by treatment group.

All tables of baseline and demographic data will be presented by sequence.

All data collected will be presented in the by-patient data listings, sorted by patient and by period and day, where appropriate.

P-values < 0.05 will be considered as statistically significant.

95% confidence interval will be calculated as appropriate.

Change From Baseline (CFB) will be summarized for efficacy and safety assessments, where Baseline is defined as Day 0.

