The quantitative secondary efficacy endpoints (6-minute walk test, Time-to-rise-from-floor, Time-to-rise-from chair, Time-to-climb-4-stairs, and Time-to-walk-10 meters) will be analyzed as the HFMSE is analyzed. The four CFB scores will be analyzed with a linear mixed model. Treatment and Sequence will be entered as fixed effects. Subject within Sequence will be entered as a random effect with a block-diagonal covariance structure. The 95% confidence interval (CI) based on this model will be presented for the difference in the Least Squares (LS) means. The analyses will be performed using SAS PROC MIXED to incorporate the random effects model.

Results from INQoL questionnaires and PEDSQL inventory of disease specific symptoms will be summarized with descriptive statistics (n, mean, standard deviation, minimum, median, and maximum) per time point (Days 0, 7, 14, 21, and 28) and CFB, using the Day 0 response as the baseline level). The subscales of the INQoL questionnaires will be similarly summarized.

Analysis of the primary efficacy endpoint will be perfored both in the FAS and in PPAS analysis set. Analysis on FAS analysis set will be considered as primary while analysis in the PPAS will be used as supportive of the FAS results.

Analysis of secondary efficacy endpoints will be performed only in the FAS analysis set.

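### Quality of life falls under a placebo-comparative secondary objective, but no treatment difference or confidence interval is planned for it

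*SAP*

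**What the plan says.** Protocol 8.1.2 states the secondary objective as assessing efficacy of "amifampridine compared with placebo by using the change from baseline in six-minute walk test, timed tests, and quality of life assessments". SAP 5.1 repeats it. The protocol synopsis introduces its list of efficacy criteria, in which quality of life is a secondary item, with "Efficacy will be assessed by comparison of amifampridine versus placebo for".

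SAP 10.11 then numbers seven secondary endpoints. Items 1 to 5 are the six-minute walk and the four timed tests. Items 6 and 7 are the change in the INQoL scores and in the PedsQL score.

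The analysis separates these. Items 1 to 5 ("6-minute walk test, Time-to-rise-from-floor, Time-to-rise-from chair, Time-to-climb-4-stairs, and Time-to-walk-10 meters) will be analyzed as the HFMSE is analyzed") go into a mixed model, and "The 95% confidence interval (CI) based on this model will be presented for the difference in the Least Squares (LS) means". INQoL and PedsQL results "will be summarized with descriptive statistics (n, mean, standard deviation, minimum, median, and maximum) per time point", both as observed and as change from Day 0. Protocol 14.6.2 has the same descriptive plan, so the SAP does not depart from the protocol here.

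On layout, SAP 10.11 has efficacy summarised by sequence and period. SAP 10.2 first calls for summaries by treatment by period and overall, and shortly after says "Summary statistics for all safety and efficacy variables will be presented by sequence".

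**The concern.** An objective phrased as a comparison should lead to a planned estimate of that comparison. For quality of life it does not: no amifampridine-minus-placebo difference, interval or test is specified, and no reason is given for treating these scores differently from the other secondary endpoints measured at the same visits.

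The crossover makes the gap matter more. With about 12 patients, divided between an adult and a paediatric instrument, what precision there is comes from comparing each patient with himself or herself. Tables of means and SDs per visit show the level of each group but not how closely a patient's two periods agree, and that agreement sets the uncertainty of the treatment difference. At stake is whether the report can state a quality-of-life effect with its uncertainty, or whether each reader must assemble one from the tables.

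**Working it through.** The documents give no quality-of-life figure to reproduce. The check is a comparison of texts, then a calculation of what the planned tables can yield and what an added model would yield.

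**1. Endpoints against analyses (SAP 10.11)**

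| Secondary endpoint | Mixed model | 95% CI for treatment difference |
|---|---|---|
| Six-minute walk | yes | yes |
| Four timed tests | yes | yes |
| INQoL scores | no | no |
| PedsQL score | no | no |

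**2. Is a point difference recoverable from the planned tables?**

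Sequence and period together identify treatment. With complete data, the crossover contrast is

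τ = [(mean AP, Period 1 − mean AP, Period 2) − (mean PA, Period 1 − mean PA, Period 2)] / 2.

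It uses only the four sequence-by-period means. On simulated data for 12 patients, 6 per sequence, the four means and the patient-level differences both gave 0.1105. So the point difference is available by hand.

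**3. Is its uncertainty recoverable?**

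Let SD be the standard deviation of one period's change from baseline (one value per patient per period), ρ the correlation between a patient's two periods, and m the number of patients per sequence.

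- One patient's period difference has variance 2·SD²·(1 − ρ).
- The mean over m patients has variance 2·SD²·(1 − ρ)/m.
- Subtracting the two sequences gives 4·SD²·(1 − ρ)/m; halving the contrast divides this by 4.
- Hence SE(τ) = SD·√((1 − ρ)/m), with 2m − 2 degrees of freedom.

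The tables give SD and m but not ρ. For m = 6, the 95% half-width could be anything from 0.91 SD (ρ = 0) to 0.29 SD (ρ = 0.9), roughly a threefold range. The interval therefore cannot be obtained from the tables.

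**4. What would a planned model deliver?**

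Inputs: about 12 patients, 6 per sequence (SAP 6.1); one instrument for adults and another for children (SAP 9.1.4). Not in the documents, so assumed: SD (results are in SD units), ρ, and how patients divide between instruments. Half-width = t × √((1 − ρ)/m):

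| Case | df | t | ρ = 0 | ρ = 0.5 | ρ = 0.7 | ρ = 0.9 |
|---|---|---|---|---|---|---|
| All 12 on one instrument, m = 6 | 10 | 2.228 | 0.91 | 0.64 | 0.50 | 0.29 |
| 6 on an instrument, m = 3 | 4 | 2.776 | 1.60 | 1.13 | 0.88 | 0.51 |

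For example, with m = 3 and ρ = 0.7: √(0.3/3) = 0.316, and 2.776 × 0.316 = 0.88 SD. With m = 3 and ρ = 0.5: √(0.5/3) = 0.408, and 2.776 × 0.408 = 1.13 SD. With m = 6 and ρ = 0.5: √(0.5/6) = 0.289, and 2.228 × 0.289 = 0.64 SD.

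**The case against.** The best defence is that describing quality of life is a deliberate choice, made consistently in protocol and SAP. This is a Phase 2a trial of about 12 patients with no power calculation, SAP 10.3 makes only the primary comparison confirmatory, and two instruments divide an already small sample. An interval nearly one SD or more either side tells the reader little. That stands as a reason to rate the point as minor. It does not explain why the objective is worded as a comparison, and a wide interval is itself the honest answer to that objective.

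Three stronger readings are tempting, and the documents do not support them.

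- A reader might infer that the objective cannot be answered at all. SAP 10.11 summarises by sequence and period, and one sentence of SAP 10.2 calls for summaries by treatment, so a descriptive comparison and a hand-calculated difference are both possible.
- A reader might infer that the crossover pairing is thrown away. SAP 10.2 also requires by-patient listings ordered by period and day, and with so few patients the individual differences, and from them a standard error, could be computed from those listings. What is absent is a planned and reported estimate with its interval.
- A reader might infer that a model would make the difference much more precise, by setting it against a comparison of the two sequences at a single visit. The plan prescribes no such reading. With complete data, the contrast from the four means has the same sampling error as the paired contrast; the model adds the statement of that error.

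**Conclusion.** The point holds as a minor mismatch between objective and analysis. Quality of life is a secondary endpoint under an objective of comparison with placebo, yet it alone among the secondary endpoints has no planned treatment difference or interval. The point difference can be recovered from the sequence-by-period summaries; its within-patient standard error and interval cannot be recovered from those tables.

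The benefit of repair is a stated estimate with its uncertainty. The sizes above rest on an assumed SD scale, an assumed correlation, an assumed division of patients between instruments, equal sequences and complete data. Under any of these cases the result is exploratory.

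**What to change.** In SAP 10.11, add a crossover mixed model for two scores: the INQoL Quality of Life score and the PedsQL score, each as defined in SAP Appendix 2, fitted separately by instrument.

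- Fixed effects: Treatment, Sequence and Period; patient as random effect. In this two-by-two design these terms are equivalent to the primary model's Treatment, Sequence and Treatment-by-Sequence. Period should be named explicitly, because the SAP's description of the secondary model lists only Treatment and Sequence.
- Report the amifampridine-minus-placebo LS-mean difference with its 95% confidence interval, labelled exploratory and without a significance claim. Keep the subscales descriptive.
- Reconcile the two layout sentences in SAP 10.2, so that it is clear whether the quality-of-life tables are by treatment or by sequence.

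The cost is two additional model runs, one per instrument, and a line in SAP 12, which now reports no changes from the protocol's analyses. SAP 4 allows revision before the unblinded analyses, and Protocol 14.8 lets the SAP prevail without an amendment. Because only the primary comparison is confirmatory, no multiplicity problem arises. The main drawback is wide intervals, and the text should say so in advance.

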#### 10.12 Safety Data

Summaries of safety data will be presented for the SAF analysis set using observed data only, i.e. without imputation. All observed safety data will be listed.

#### 10.12.1Adverse Events

For this protocol, a reportable AE is any untoward medical occurrence (e.g. sign, symptom, illness, disease or injury) in a patient administered the IP or other protocol-imposed intervention, regardless of attribution. This includes:

- AEs not previously observed in the patient that emerge during the study.
- Pre-existing medical conditions judged by the Investigator to have worsened in severity or frequency or changed in character during the study.
- Complications that occur as a result of non-drug protocol-imposed interventions.

An adverse drug reaction is any AE for which there is a reasonable possibility that the IP caused the AE. "Reasonable possibility" means there is evidence to suggest a causal relationship between the IP and the AE.

Whenever possible, it is preferable to record a diagnosis as the AE term rather than a series of terms relating to a diagnosis.

The study period during which all non-serious AEs will be reported begins after the first administration of study drug through the termination visit or at the early termination visit. After informed consent but prior to initiation of study treatment, only SAEs associated with any protocolimposed interventions will be reported. The criteria for determining, and the reporting of SAEs is provided in Protocol Section 10.2.

The Investigator should follow all unresolved AEs until the events are resolved or stabilized, the patient is lost to follow-up, or it has been determined that the study treatment or participation is not the cause of the AE. Resolution of AEs (with dates) should be documented on the appropriate CRF page(s) and in the patient's medical record.

The Investigator responsible for the care of the patient or qualified designee will assess AEs for severity, relationship to IP, and seriousness (refer to Protocol Section 10.2 for SAE definition). Severity (as in mild, moderate or severe headache) is not equivalent to seriousness, which is based on patient/event outcome or action criteria usually associated with events that pose a threat to a patient's life or functioning. Seriousness (not severity) serves as a guide for defining regulatory reporting obligations.

The Investigator will determine the severity of each AE using grades defined in Table 1 (the event will be recorded on the source documents and AE CRF). Events that are Grades 4 and 5 are serious events and require completion of both an SAE form and AE CRF.

**Table 1 - Categories of Severity for Adverse Events** 

Severity	Description	
Grade 1	Mild; asymptomatic or mild symptoms; clinical or diagnostic observations only; intervention not indicated.	
Grade 2	Moderate; minimal, local or noninvasive intervention indicated; limiting age-appropriate instrumental ADL*.	
Grade 3	Severe or medically significant but not immediately life-threatening; hospitalization or prolongation of hospitalization indicated; disabling; limiting self-care ADL**.	
Grade 4	Life-threatening consequences; urgent intervention indicated.	Note: Grade 4 and 5 adverse events should
Grade 5	Death related to AE.	always be reported as serious adverse events

Activities of Daily Living (ADL)

\* Instrumental ADLs refer to preparing meals, shopping for groceries or clothes, using the telephone, managing money, etc.

\*\*Self-care ADLs refer to bathing, dressing and undressing, feeding self, using the toilet, taking medications, and not bedridden.

A treatment-emergent adverse event (TEAE) is any AE that emerges after randomization having been previously absent, or worsens relative to the previous periods. All AEs will be coded using the Medical Dictionary for Regulatory Activities (MedDRA), Version 23.0. All treatment-emergent adverse events (TEAEs) will be summarized by the treatment at the time of onset. Counts and percentages will be presented by treatment for each observed system organ class (SOC) and preferred term (PT) as defined in MedDRA. A patient having more than one TEAE with the same PT in a given time period will be counted only once in the incidence calculation for that PT for that time period. Similarly, if a patient has more than one TEAE in the same SOC in a given time period, the patient will be counted only once in the total number of patients with a TEAE for that SOC for that time period. TEAEs will summarized only for the treatment at onset unless it worsens at subsequent period(s) or recurs after having resolved at a previous period; in each of these situations, the TEAE will be considered a new TEAE and summarized for both treatments.

Each TEAE will be assessed with respect to severity and relationship to treatment. The relationship of an AE will be recorded using the specified relationship categories described in Table 2.

Table 2 - Description of relationship to adverse events categories

Relationship	
Category	Description
Not Related	Exposure to the IP has not occurred
	OR
	The administration of the IP and the occurrence of the AE are not
	reasonably related in time
	OR
	The AE is considered likely to be related to an etiology other than the
	use of the IP; that is, there are no facts [evidence] or arguments to
	suggest a causal relationship to the IP.
Possibly	The administration of the IP and the occurrence of the AE are
Related	reasonably related in time
	AND
	The AE could be explained equally well by factors or causes other
	than exposure to the IP.
Probably	The administration of IP and the occurrence of the AE are reasonably
Related	related in time
	AND
	The AE is more likely explained by exposure to the IP than by other
	factors or causes.

The following summary tables will be provided:

1. An overview of TEAEs including the number of TEAEs, related TEAEs, TESAEs, related TESAEs, TEAEs leading to premature discontinuation, TEAEs leading to hospitalization, life-threatening TEAEs, number of patients with at least one TEAE, at least one related TEAE, at least one TESAE, at least one TEAE leading to premature discontinuation, at least one TEAE leading to hospitalization, at least one life-threatening TEAE, and at least one TEAE leading to death

- 2. Summary of all TEAEs by treatment group, Primary SOC and PT
- 3. Summary of all related TEAEs by treatment group, Primary SOC and PT
- 4. Summary of all TESAEs by treatment group, Primary SOC and PT
- 5. Summary of all related TESAEs by treatment group, Primary SOC and PT
- 6. Summary of all TEAEs leading to hospitalization by treatment group, Primary SOC and PT
- 7. Summary of all life-threatening TEAEs by treatment group, Primary SOC and PT
- 8. Summary of all TEAEs leading to premature discontinuation by treatment group, Primary SOC and PT
- 9. Summary of all TEAEs by treatment group, Primary SOC and PT and maximum severity

The following individual data listings will be produced:

- 1. A listing of all TEAEs
- 2. A listing of all TESAEs
- 3. A listing of all IMP related TEAEs
- 4. A listing of all IMP related TESAEs
- 5. A listing of all TEAEs leading to hospitalization
- 6. A listing of all life-threatening TEAEs
- 7. A listing of TEAEs leading to premature discontinuation
- 8. A listing of all TEAEs leading to death
- 9. A listing of all AEs started before the first dose of study drug intake
- 10. A listing of all AEs started after the first dose of study drug intake but before the date of randomization (Day 0)

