14.5 Safety Analysis

Prior to analysis, all AEs will be coded using the MedDRA coding dictionary. Based on these coded terms, TEAEs and SAEs will be summarized using system organ class and preferred terms, as well as by relationship to treatment. All AEs will be listed, regardless of whether they were study treatment related.

Vital signs will be summarized using descriptive statistics (mean, standard deviation, median, minimum, maximum, and number of non-missing observations) by time point. Changes from baseline will also be summarized by post-dose time point.

Clinical laboratory parameters will be summarized using descriptive statistics (mean, standard deviation, median, minimum, maximum, and number of non-missing observations) by time point. Changes from baseline will also be summarized by post-dose time point. In addition, a shift table will be constructed to show the shifts in laboratory results by parameter relative to the normal ranges. The number and percentage of subjects with the following shifts will be presented: normal/normal, normal/low, normal/high, low/low, low/normal,

Page 55

low/high, high/low, high/normal, and high/high. Similar shift tables will also be constructed for physical exam results. ECG results will be summarized in a shift table with the following shifts presented: normal/normal, normal/abnormal, abnormal/normal and abnormal/abnormal. A table of descriptive statistics for QTc interval by treatment, day and period will be created.

Additional safety analyses may be performed as described in the SAP for the study.

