## 10.1 Analysis Populations

The following analysis populations have been defined for this clinical study:

- a) Enrolled Population (EP): all patients who provided informed consent for this study.
- b) **Safety Population (SAF)**: the safety population consists of all subjects who are enrolled in the study and have received at least one dose of amifampridine and includes subjects who begin the Run-in period regardless of whether they are randomized to double blind medication on Day 0.
- c) Full Analysis Set (FAS): this population consists of all randomized subjects who receive at least one dose of IP (amifampridine or placebo) and have at least one post-treatment efficacy assessment. Subjects will be compared for efficacy according to the treatment to which they were randomized, regardless of the treatment actually received.
- d) **Per-Protocol Population (PPAS)**: this population is a subset of the FAS population, excluding subjects with major protocol deviations. The PPAS population will include all FAS subjects who:
  - Have no major protocol deviations or inclusion/exclusion criteria deviations that might potentially affect efficacy, and
  - Subjects who took at least 80% of the required treatment doses.

The PPAS population will be determined before database lock and unblinding subject treatment codes.

The FAS population will be the primary analysis set for all effectiveness analyses. The safety population will be used for the analysis of all safety variables and baseline characteristics. The PPAS population will be used for selected effectiveness analyses. The results obtained in PPAS population set will be seen as supportive of those obtained in the FAS population.

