# 10.10.2 Duration of Treatment and Compliance

Duration of treatment during the open-label period will be summarized for the Safety Population. The duration of treatment during the open-label run-in period is the date of Day 0 minus date of first study dose+1.

Duration of treatment during the double-blind periods will be summarized for the Safety Population by treatment and by period and pooled.

For Period 1, the duration of treatment is the (date of Day 14 minus date of Day 0)+1; for patients who discontinue during Period 1, the duration of treatment during Period 1 is the (date of the last dose during Period 1 minus the date of Day 0) +1.

For Period 2, the duration of treatment is the (date of Day 28 minus date of Day 14)+1; for patients who discontinue during Period 2, the duration of treatment during Period 2 is the (date of the last dose during Period 2 minus the date of Day 14)+1.

The overall duration during the double-blind periods will be obtained for each treatment by adding the durations for the periods during which the patient received each treatment.

Compliance is 100%\*(Number consumed)/(Number prescribed). "Number consumed" is from Study Drug Accountability and "Number prescribed" is number of tablets to have been taken daily duration.

Compliance during the double-blind periods will be summarized for the Safety Population by treatment and by period. The compliance during the double-blind periods will be obtained for each treatment by performing the same calculations for the periods during which the patient received each treatment.

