## 14 Programming Conventions for Outputs

Outputs will be presented according to the standard SPARC's layout of tables and line listings.

**Dates & Times:** depending on data available, dates and times will take the form ddmmmyyyy hh:mm (i.e. 01JAN2019 10:20)

Spelling Format: English US.

Listings: all listings will be ordered by the following (unless otherwise indicated in the template):

- Site ID
- Randomization number
- Sequence (where applicable)
- Study visit
- Study treatment
- Date and hours (where applicable)
- For listings where non-randomized patients are included, these will appear in a category after the randomized treatment groups labelled 'Not Randomized'.

In all listings missing data will be reported, according to the variable type, as follows:

- Character variables and dates will be presented as empty fields
- Numerical variables will be presented with a "-"

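### AE tables count onset only from randomization, so events that begin in the open-label amifampridine run-in get no incidence summary

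*SAP*

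**What the plan says.** SAP 10.12.1 sets the definition: "A treatment-emergent adverse event (TEAE) is any AE that emerges after randomization having been previously absent, or worsens relative to the previous periods." TEAEs are assigned to the treatment at onset. If a TEAE worsens in a later period, or comes back after resolving, "in each of these situations, the TEAE will be considered a new TEAE and summarized for both treatments."

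The same section lists nine AE summary tables, each restricted to TEAEs or treatment-emergent SAEs (TESAEs). It also lists ten data listings. Eight are TEAE or TESAE only, the ninth covers events before the first dose, and the tenth is described as "A listing of all AEs started after the first dose of study drug intake but before the date of randomization (Day 0)."

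Other parts of the plan treat the run-in as part of the safety evidence:

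- SAP 10.1: the safety population "includes subjects who begin the Run-in period regardless of whether they are randomized to double blind medication on Day 0."
- SAP 10.12: "Summaries of safety data will be presented for the SAF analysis set using observed data only."
- SAP 10.10.2: "Duration of treatment during the open-label period will be summarized for the Safety Population."
- Protocol Table 1, footnote h: non-serious AEs are collected from Day 1 of run-in, and SAEs from consent.
- SAP 14: for listings that include patients never randomized, "these will appear in a category after the randomized treatment groups labelled" Not Randomized.

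The protocol does not define a TEAE. Its Synopsis confines the safety analysis to TEAEs, while Protocol 14.5 says "TEAEs and SAEs will be summarized using system organ class and preferred terms, as well as by relationship to treatment."

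**The concern.** The first primary objective (Protocol 8.1.1) is to characterize overall safety and tolerability compared with placebo. The run-in holds the planned dose titration and, on the planned durations, most of each patient's time on amifampridine. Patients who cannot reach and hold a stable dose leave before randomization. If AE incidence is tabulated only from randomization, the report gives a denominator of exposure for the run-in but no AE rates to set beside it. There would be no breakdown by system organ class and preferred term, relatedness, seriousness or severity. A reader of the tables would see the AE profile of patients already shown to tolerate a stable dose, and would have to build the run-in profile by hand from a listing.

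**Working it through.** **Count of outputs (SAP 10.12.1).** Summary tables limited to TEAEs or TESAEs: 9 of 9. Listings so limited: 8 of 10. Listing 9 is pre-dose, and listing 10 is the only AE output named for run-in onset.

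**Where each kind of event goes under the written rules.**

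- Starts and resolves in run-in: onset is before randomization, so it enters no table and appears in listing 10.
- Starts in run-in and continues unchanged into a blinded period: it was not previously absent and is not worse, so it enters no table.
- Starts in run-in and worsens after randomization: it is a TEAE and is tabulated.
- Starts in run-in, resolves, and recurs after randomization: unclear, because the recurrence rule is written for something already called a TEAE.
- Pre-existing condition that worsens during run-in: the worsening clause is not expressly tied to randomization, so this could be read as a TEAE. No run-in category is named for the tables to hold it.
- AE in a patient never randomized: it cannot meet the onset clause. Apart from the worsening reading just given, it appears in listings only.

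Serious events follow the same route, because the SAE tables are TESAE tables.

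**Share of planned amifampridine time before the onset window.** The plan gives no figure of its own to reproduce. The inputs are:

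- treatment duration of about 8 weeks (Protocol Synopsis, Duration of Treatment);
- participation of at least 60 days excluding screening (Protocol 9.1.1);
- 28 double-blind days, of which 14 are on amifampridine (Protocol 9.1.1).

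Formula: share = run-in days / (run-in days + 14).

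- From 8 weeks: 8 × 7 − 28 = 28 run-in days; 28 / (28 + 14) = 28/42 = 66.7%.
- From 60 days, if participation is read as dosing time: at least 60 − 28 = 32 run-in days; 32 / (32 + 14) = 32/46 = 69.6% or more.
- Sensitivity, with assumed run-in lengths: 21 days gives 21/35 = 60.0%; 42 days gives 42/56 = 75.0%.
- Never randomized: 100%. The documents do not say how many such patients to expect.

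The run-in may be extended for titration (Protocol 9.1.1), so there is no fixed upper limit.

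**Denominator.** SAP 10.12 names only the safety population for safety summaries. If that were used as N for the by-treatment AE percentages, patients never randomized would sit in the denominator without being able to contribute a post-randomization onset. The SAP text does not say which N applies.

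**The case against.** The best defence is that anchoring TEAEs to randomization is right for a comparison with placebo. The run-in has no placebo arm, and listing 10 shows that the run-in was considered. With about 12 randomized patients, a complete listing shows every event, so table against listing is partly a matter of presentation. The first part of that stands, and the fix leaves the double-blind tables in place. The second part stands only in part, because a listing gives no incidence, no denominator and no summary by term, severity or relatedness.

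A reader might also infer stronger things that the documents do not support:

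- *Run-in safety goes unreported.* It does not. All observed safety data are listed, and ECG, physical-examination and laboratory summaries reach Day 0. Those summaries are mainly by sequence, which never-randomized patients lack, but SAP 10.2 also mentions an overall presentation, and the table shells are not in the text available.
- *Events that stop a patient before randomization are visible only in a listing.* SAP 10.10.1 plans counts of premature dosing discontinuation with the primary reason, and that sentence is not limited to randomized patients. Run-in stops may therefore be tabulated there, though not as AEs.
- *No titration event can reach a table.* The worsening clause may admit some.
- *The blinded amifampridine column is understated.* This needs a run-in reaction to persist unchanged across randomization. Protocol 7.4.3 calls the common AEs typically transient, run-in events persisting into placebo are dropped too, and the size cannot be derived from the documents.
- *The SAP departs from the protocol.* The protocol leaves TEAE undefined, and its Synopsis limits the safety analysis to TEAEs. The wording of Protocol 14.5 and of the recurrence rule calls for clarification only and carries no weight here.

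**Conclusion.** The point holds as a reporting gap. As written, none of the nine AE tables gives an incidence for events that begin in the run-in and do not later worsen (or arguably recur), although the safety population and the exposure summary both include the run-in. About two thirds of a randomized patient's planned amifampridine time lies before the onset window, and all of it for a patient never randomized. The 66.7% rests on the approximate 8-week duration, and the 69.6% on treating participation as dosing time. Neither says what share of AEs is affected. This omission does not touch the randomized comparison with placebo. It does limit how well the report can characterize overall tolerability, and it is cheap to put right before unblinding.

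**What to change.** 1. Keep the randomization-anchored double-blind TEAE tables. State their denominator as patients dosed with that treatment in the double-blind phase.
2. Add a separate descriptive run-in AE summary by system organ class and preferred term, with onset on or after the first run-in dose and N = all safety-population patients. It should show all, related and serious events, events leading to discontinuation, and maximum severity. Do not pool it with the blinded amifampridine column.
3. Optionally, add one supportive table of events present in each double-blind period, including those ongoing from run-in.
4. For clarity, say whether the recurrence rule reaches run-in events and how run-in SAEs are summarized.

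The cost is about six descriptive tables (five for the run-in and the optional one) and a few sentences of SAP text. The AEs are already collected from run-in Day 1. The downside is that the reported AE profile may look less favourable.
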